### 2.7.2 Subject Replacement Rules

Subjects who are withdrawn due to no stool sample provided within 30 days of enrollment or due to colonoscopy procedure not done may be replaced.

## 2.8 Effectiveness Analysis

### 2.8.1 Effectiveness Parameters and Hypotheses

The primary effectiveness endpoint of this study is the specificity to advanced neoplasia of the mt-sDNA (Cologuard) test in the 45-49 age group in an average risk population, using colonoscopy with histopathology (if appropriate) as the reference method. The primary effectiveness analysis requires the one-sided 97.5% confidence lower bound of the specificity of mt-sDNA (Cologuard) test to exceed 85.0%.

Subjects with colonoscopic findings in categories 3-6 will be included in the specificity analysis as disease status negative outcomes for the primary endpoint calculation. Thus, specificity to advanced neoplasia (AN) will be calculated for the primary endpoint evaluation. The colonoscopically 'negative' population (category 6) will include those subjects with a colonoscopy showing no findings of colorectal neoplasia, non-neoplastic disease, and/or hyperplastic polyps  $\leq 1$  cm in diameter.

Subjects with no findings on the colonoscopy, no photographic evidence of cecal intubation and no documentation of cecal intubation in the report, will be excluded from Per Protocol analyses. Subjects found to have occult inflammatory bowel disease (IBD) on colonoscopy will be excluded from all analyses. Subjects with an invalid mt-sDNA (Cologuard) test will be excluded from the ITS and Per Protocol population. All excluded cases will be assessed for bias.

Subjects with colonoscopic/histopathologic findings in category 1 (confirmed colorectal cancer cases) will be considered to have a positive outcome and will be included in the CRC sensitivity calculations. Note:

Due to the low prevalence of CRC in the Age 45-49 group, there will likely be no CRC prospectively enrolled in the study, so no primary endpoints will be designed around CRC sensitivity. CRC sensitivity (if any CRC cases are present) will be analyzed as an exploratory endpoint.

Similarly, due to the low prevalence of AA in the Age 45-49 group, there may only be approximately 29 subjects\* with colonoscopic/histopathologic findings in category 2 (advanced adenomas) prospectively enrolled in the study, so no primary endpoints will be designed around AA sensitivity. AA sensitivity will be calculated as an exploratory endpoint. To determine sensitivity for histopathologically-confirmed advanced adenomas, subjects with colonoscopic findings in Category 2 will be considered to have a positive outcome (for the AA sensitivity calculation) and, as above, subjects with colonoscopic findings in categories 3-6 will be considered to have a negative outcome.

\*Advanced adenoma prevalence among never-screened individuals aged 45-49 years may be derived, based on simulation results, to be 3.92%.  $731 \times 3.92\% = 29$  [1].

The primary effectiveness endpoint analysis for mt-sDNA (Cologuard) test specificity will be performed using an exact binomial (Clopper-Pearson) test to compute the one-sided 97.5% confidence lower bound; the lower bound must exceed 85.0%. Specificity will be assessed for a random sample of approximately 731 subjects with non-advanced neoplasia and negative colonoscopies.

Rejecting the null hypothesis will demonstrate the Specificity in the Age 45-49 group is no worse than the pre-specified lower bound limit established in the DeeP-C protocol.

The parameters below are all single point in time following last subject enrolled and all study procedures complete. This is not meant to be an exhaustive list: additional exploratory analyses may be performed.

Parameter	Hypothesis/ Analysis*
Endpoint 1 (Primary):	Evaluation of Specificity (Category 3-6) in the Age 45-49 group. H0: $P \leq P_0$ (85.0%) H1: $P = P_1 > P_0$ (85.0%)
Endpoint 2 (Exploratory):	Analysis of sensitivity for CRC (if applicable)
Endpoint 3 (Exploratory):	Analysis of Sensitivity for AA. [REDACTED]
Endpoint 4 (Exploratory):	[REDACTED]
Endpoint 5 (Exploratory):	[REDACTED]
Endpoint 6 (Exploratory):	[REDACTED]
Endpoint 7 (Exploratory):	[REDACTED]
Endpoint 8 Exploratory):	[REDACTED]

	[REDACTED]
Endpoint 9 (Exploratory):	[REDACTED]
Endpoint 10 (Exploratory):	[REDACTED]
Endpoint 11 (Exploratory):	The Odds Ratio, NLR, PLR, NPV, PPV and diagnostic yield for the mt-sDNA test will be estimated. [REDACTED]
Endpoint 12 (Exploratory):	[REDACTED]
Endpoint 13 (Exploratory):	[REDACTED]
Endpoint 14 (Exploratory)	[REDACTED]
Endpoint 15 (Exploratory)	[REDACTED]
Other Outcome 1:	[REDACTED]
Other Outcome 2:	[REDACTED]

	[REDACTED]
Other Outcome 3:	The rate of no valid mt-sDNA (Cologuard) test result
Other Outcome 4:	[REDACTED]
Other Outcome 5:	[REDACTED]

\*Hypothesis tests will be limited to the primary effectiveness endpoint.

Additionally, baseline demographic information will be presented for all enrolled, and by specificity and sensitivity subsets.

The measures of screening accuracy are defined as follows:

mt-sDNA (Cologuard) Test	Reference Test (Colonoscopy)	
	CRC+	CRC-
sDNA +	A (TP)	B (FP)
sDNA -	C (FN)	D (TN)

Definitions	
Advanced Neoplasia (AN)	Colonoscopic findings that include colorectal cancer (CRC) (category 1) and advanced adenoma (AA) (category 2).
Non-advanced neoplasia (NAN)	Colonoscopic findings $\leq$ 1.0 cm that exclude colorectal cancer (CRC) and advanced adenoma (AA) and include categories 3 – 5.
Sensitivity (Se)	$TP/(TP + FN)$
Specificity (Sp)	$TN/(TN+FP)$
False positive fraction (FPF)	$FP/(TN+FP)$
Odds ratio	$(TP/FP)/(FN/TN)$
Negative likelihood ratio	$(1-Se)/(Sp)$
Positive likelihood ratio	$Se/(1-Sp)$
Negative Predictive Value	$TN/(FN+TN)$ and/or $[Sp*(1-Prevalence)]/[(1-Se)*(Prevalence+Sp*(1-Prevalence))]$ .
Positive Predictive Value	$TP/(TP+FP)$ and/or $(Se*Prevalence)/[Se*Prevalence+(1-Sp)*(1-Prevalence)]$

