#### 6.2 Other Outcomes

Other outcomes to be assessed include the following

- Sensitivity for CRC + advanced adenoma
- The positive and negative predictive values
- The positive and negative likelihood ratios (PLR and NLR, respectively)
- The distribution of colorectal epithelial lesions (by Category) among positive mt-sDNA test (Cologuard) subjects
- The rate of no mt-sDNA (Cologuard) result

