#### 12.4.1 Additional Analysis

NPV, PPV, Odds Ratio, NLR, PLR and diagnostic yield for the 45-49 age group will be estimated
using the observed study specificity and different assumptions regarding prevalence of CRC/AA
and assumptions regarding sensitivity to CRC/AA.

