#### 12.6.3 Determination of Diagnostic Accuracy

These data will be presented in the form of 2 x 2 tables, which will be presented separately for colorectal cancer (CRC), Advanced adenoma (AA), and advanced colorectal neoplasia (CRC+AA). Point estimates of sensitivity and specificity, along with Clopper-Pearson confidence intervals will be used to assess performance against study endpoint.

Results of study will be displayed in 2x2 tables (for CRC, AA, and combined) as shown below:

Table 2: Outcome for all CRC (AA, or combined) subjects

EXACT	Reference Test (Colonoscopy)		
Test	CRC+	CRC-	
sDNA +	A (TP)	B (FP)	
sDNA -	C (FN)	D (TN)	

The table includes the number of true positives (TP: those that have the disease and test positive), false positives (FP: those that do not have the disease and test positive), false negatives (FN: those that do have the disease and test negative) and true negatives (TN: those that do not have the disease and test negative).

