#### **2.10.1 Multiple Comparisons / Multiplicity**

No p-value adjustments will be performed for multiple testing. A p-value will be computed for the primary effectiveness endpoint. The other effectiveness endpoints may include p-values in their evaluation but are considered exploratory endpoints.

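### SAP 2.8.1: a misplaced parenthesis makes the prevalence-based NPV formula wrong; at the plan's own specificity and prevalence it exceeds 100% once sensitivity passes about 4.2%

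*SAP*

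**What the plan says.** NPV is a planned outcome in both documents. Protocol 6.2 lists "The positive and negative predictive values", and SAP Endpoint 11 (exploratory) states "The Odds Ratio, NLR, PLR, NPV, PPV and diagnostic yield for the mt-sDNA test will be estimated". Protocol 12.4.1 says how these measures are to be obtained: "using the observed study specificity and different assumptions regarding prevalence of CRC/AA", together with assumed values of sensitivity.

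The NPV row of the Definitions table in SAP 2.8.1 offers TN/(FN+TN) and/or a prevalence-based expression whose core is "Sp*(1-Prevalence)]/[(1-Se)*(Prevalence+Sp*(1-Prevalence" (the outermost bracket at the left and the closing brackets at the right are cut off in this quote). In the SAP the expression ends with two closing parentheses before the final square bracket. The row below gives PPV in the same style: "Se*Prevalence)/[Se*Prevalence+(1-Sp)*(1-Prevalence".

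Protocol 12.1.1 prints the same NPV expression with only one closing parenthesis before the final square bracket.

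**The concern.** Write P for prevalence. Among all subjects, the false-negative share is (1−Se)P and the true-negative share is Sp(1−P), so the NPV denominator must be their sum. The SAP's parenthesis opens before prevalence and closes after the true-negative term, so (1−Se) also shrinks the true negatives. The two expressions offered as alternatives in one row are then different quantities.

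The prevalence-based form is the natural one for Protocol 12.4.1, which combines observed specificity with assumed prevalence and assumed sensitivity. It matters most for cancer. Both documents expect that probably no CRC will be enrolled. With no CRC cases FN is 0, and the count-form NPV for CRC computed from observed counts is 100% by construction. The informative CRC figure would have to come from assumed inputs. A programmer who codes the SAP expression literally gets impossible values at any realistic sensitivity.

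**Working it through.** The documents state no numerical NPV, so there is no NPV figure to reproduce. The related count does reproduce: 731 × 3.92% = 28.7, which the plan rounds to 29.

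**Inputs**
- Specificity Sp = 92.2%: alternative proportion, Protocol 12.3.
- Prevalence P = 3.92%: advanced adenoma, Protocol 12.2 and SAP 2.8.1.
- Sensitivity Se: not given, because Protocol 12.4.1 leaves it to be assumed. The values below are illustrative.

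**Parentheses.** Counting round parentheses in the full expression gives 4 opening and 4 closing in the SAP, and 4 opening and 3 closing in the protocol. The SAP version can be evaluated; the protocol version cannot.

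**Formulas**
- Printed (SAP): Sp(1−P) / [(1−Se)(P + Sp(1−P))]
- Correct: Sp(1−P) / [(1−Se)P + Sp(1−P)]
- Correct denominator minus printed denominator = Se·Sp(1−P), which is zero only at Se = 0.

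**Common terms.** Sp(1−P) = 0.922 × 0.9608 = 0.88586, and P + Sp(1−P) = 0.92506. The printed form is therefore (0.88586/0.92506)/(1−Se) = 0.9576/(1−Se).

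**Worked case, Se = 0.40**
- Printed: 0.88586 / (0.60 × 0.92506) = 159.6%.
- Correct: 0.88586 / (0.60 × 0.0392 + 0.88586) = 0.88586/0.90938 = 97.4%.
- Check by counts: a 2×2 table built from the same Se, Sp and P gives TN/(FN+TN) = 97.4%.
- Check by the plan's own NLR: (1−Se)/Sp = 0.60/0.922 = 0.6508, and 1/[1 + 0.6508 × 0.0392/0.9608] = 97.4%.

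| Assumed Se | Printed form | Correct NPV |
|---|---|---|
| 0% | 95.8% | 95.8% |
| 2% | 97.7% | 95.8% |
| 5% | 100.8% | 96.0% |
| 20% | 119.7% | 96.6% |
| 30% | 136.8% | 97.0% |
| 40% | 159.6% | 97.4% |
| 50% | 191.5% | 97.8% |
| 90% | 957.6% | 99.6% |

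At Se = 100% the printed form divides by zero; the correct NPV is 100%.

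**Threshold.** Setting the printed form equal to 1 gives Se* = P/[P + Sp(1−P)] = 0.0392/0.92506 = 4.24%. The range is:
- at Sp = 92.2%: 0.54% for P = 0.5%, rising to 6.5% for P = 6%;
- at P = 3.92%: 4.6% for Sp = 85%, falling to 4.1% for Sp = 95%.

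**Control.** The PPV row is grouped correctly. At Se = 0.40 its prevalence form and TP/(TP+FP) both give 17.3%.

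**The case against.** The strongest reply is that this is a typographical slip with no effect on any decision, and most of that stands. The SAP says "Hypothesis tests will be limited to the primary effectiveness endpoint", and SAP 2.10.1 says the other effectiveness endpoints "may include p-values in their evaluation but are considered exploratory endpoints". The primary specificity analysis, PPV, NLR and PLR are untouched. No figure stated in the plan changes. The count form in the same row is right, and applying it or the NLR to assumed inputs recovers the correct NPV. An NPV above 100% would be hard to miss.

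A second reply is that the SAP's second closing parenthesis might come from the reading of the PDF. In that case the expression would be malformed rather than wrong, and the values above 100% would not follow from it. This cannot be excluded from the text alone. But the stray opening parenthesis stands in both documents, so an artefact is an unlikely explanation for the error as a whole. Under either reading neither document prints a usable prevalence-based NPV, and the correction is the same.

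A third reply is that use of this expression is not certain. The row says and/or, Protocol 12.4.1 cites no formula, and part of Endpoint 11 is redacted. Protocol 12.6.3 states "These data will be presented in the form of 2 x 2 tables", from which an observed NPV could be read by the count form, although that section does not itself mention NPV. These points limit the impact. They do not make the definition correct, and a prespecified formula should not depend on a programmer noticing that it fails.

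**Conclusion.** The error is real and minor. As printed in the SAP, the prevalence-based NPV overstates the true value for every sensitivity above zero, and it exceeds 100% beyond a threshold of a few percent. That threshold is 4.24% at Sp = 92.2% and P = 3.92%; it moves with the assumed inputs, as shown, but stays far below any sensitivity one would realistically assume. The sizes rest on the SAP's parentheses being as read and on illustrative sensitivities, because the plan gives none. The 3.92% is an advanced-adenoma prevalence, so the figures at high sensitivity illustrate the formula and are not forecasts. The algebraic fault depends on none of these values.

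**What to change.** In both Protocol 12.1.1 and SAP 2.8.1, replace the prevalence-based expression with

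NPV = [Sp × (1−Prevalence)] / [(1−Se) × Prevalence + Sp × (1−Prevalence)].

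This means deleting the opening parenthesis before prevalence in both documents, and its matching closing one in the SAP. The corrected form equals TN/(FN+TN) at every sensitivity tested and never exceeds 100%. It changes no data collection, no sample size and no primary analysis. The only cost is the edit. If NPV has already been programmed, compare the code once with the count form.

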## 2.9 Subject Accounting

All subjects will be followed from enrollment to study completion or withdrawal. A correction will be made for the number of subjects lost to follow-up during the study. Age, gender, race, smoking status and ethnicity will be assessed as explanatory covariates in exploratory analyses. These analyses include sensitivity and specificity, negative and positive likelihood ratio (NLR, PLR), and cumulative risk of a false or true positive (cFPR, cTPR). As noted in section 2.8.1, the prevalence of CRC and AA in the study

population is expected to be low, so certain exploratory analyses may not be performed due to this limitation.

### 2.9.1 Handling of Missing Data

All subjects will be used for all analyses, when possible, with the caveat of limitations existing due to eligibility considerations, the availability of a valid mt-sDNA test result, and the availability of a reportable colonoscopy reference test result. Additional considerations follow:

- If a subject is found to have occult inflammatory bowel disease (IBD) on colonoscopy, the subject will be excluded from all analyses; this may not be known in advance of performing the colonoscopy.
- It is possible for the mt-sDNA (Cologuard) test to not be valid for multiple reasons; this results in the need to exclude such subjects from analysis because it will not be known if the subject was positive or negative—there is no way to infer or impute the outcome.
- The colonoscopy needs to be complete prior to data base lock and it must be reportable. If the colonoscopy is not reportable, the subject cannot be used for any analyses; calculations of sensitivity and specificity require a reference-test result.

Performance estimates from this study can be adjusted for missing mt-sDNA results by assuming that within each histologic category, the distribution of mt-sDNA results, when available, would be expected to have the same distribution as mt-sDNA non-missing results (i.e. missing at random).

### 2.9.2 Study Completion

Subjects who have a mt-sDNA (Cologuard) test and complete colonoscopy will be considered complete with respect to study procedure requirements. The date of study completion is the date of colonoscopy.

The study will end when all subjects have completed or discontinued including withdrawals.

### 2.9.3 Handling of Withdrawals

Subjects may be withdrawn from the study by any of the following mechanisms:

1. Voluntary withdrawal of consent to participate by the subject at any time during the study.
2. Determination by the clinical investigator that it is in the best interest of the subject.
3. Determination by the Sponsor it is in the best interest of the subject or study.
4. Stool sample not provided.
5. Colonoscopy procedure is not performed.

All data available from enrollment to subject withdrawal will be collected unless the subject withdraws consent from the study. Data for all study visits will be collected for subjects who discontinue participation but who do not withdraw consent. Withdrawal of consent must be documented by site personnel in the subject source record.

## 2.10 Data Monitoring

Once subject enrollment is initiated and data become available, data review will be completed on a monthly basis by the statistical and clinical affairs teams to provide ongoing monitoring feedback and continuous data cleaning. Due to the low prevalence of CRC in the Age 45-49 group, there will likely be no CRC prospectively enrolled in the study, so no endpoints will be designed around CRC sensitivity. Similarly, due to the low prevalence of AA in the Age 45-49 group there may only be approximately 29 subjects [1] with colonoscopic/histopathologic findings in category 2 (advanced adenomas) prospectively enrolled in the study, so no endpoints will be designed around AA sensitivity.

The study will not be stopped for efficacy under any circumstances so no alpha-spend is planned.

The study will be further monitored to assure appropriate clinical management of subjects and rigor of study conduct in the following ways:

- Independent central pathologist(s) may review surgery and histopathology reports.
- The Investigator or the Investigator's designees are required to complete all data entry into the EDC system. Every effort should be made to respond to all monitoring and/or data management questions in the EDC system, as completion of the data is required by the protocol. A unique ID number (site specific) will identify each subject along with subject's initials. Completed data is needed in order to provide statistical analysis for each subject. All data should be promptly entered once obtained by the site. The Principal Investigator is responsible for reviewing and signing the EDC system as required and ensuring 21 CFR Part 11 adherence.
- A designated study Clinical Research Associate (CRA) will periodically inspect relevant study records at the clinical site to ensure the study is being conducted in accordance with FDA regulations, the signed investigator agreement, and the approved investigational plan/protocol. The CRA will also ensure the EDC system is being completed accurately. The designated CRA assigned to the site will perform visits as per the Study Monitoring Plan.
- A representative of Exact Sciences will monitor the study at regular intervals throughout the course of the trial, per the Monitoring Plan. On-site monitoring of the Investigator's facilities will aid in assuring compliance to the protocol and applicable laws and regulations. Any deficiencies noted during the monitoring visits will be discussed with the Investigator, and the corrective action(s) to be taken will be agreed upon and documented.

#### **2.10.1 Multiple Comparisons / Multiplicity**

No p-value adjustments will be performed for multiple testing. A p-value will be computed for the primary effectiveness endpoint. The other effectiveness endpoints may include p-values in their evaluation but are considered exploratory endpoints.

#### **2.10.2 Examination of Subgroups**

Results for exploratory effectiveness endpoints include analyses by gender, age, race, ethnicity and smoking status.

#### **2.10.3 Supplementary Analyses**

Supplementary, emergent, and exploratory analyses may be conducted.

### **3 SAFETY EVALUATION**

#### **3.1 Extent of Exposure**

Summary of exposure is by subject according to the number of Cologuard tests performed. Exposure will be characterized as the total number of mt-sDNA (Cologuard) tests. Exposure will not be characterized by start/stop dates or days on study.

#### **3.2 Adverse Events**

An adverse event (AE) is any unfavorable or unintended sign, symptom, or disease temporally associated with the use of an investigational product or protocol-imposed intervention, regardless of attribution.

[REDACTED]. [REDACTED]  
The liquid buffer/liquid preservative in the quantities provided is non-toxic. An AE may be investigated as an Unanticipated Adverse Device Effect (UADE), if applicable.

Adverse events commonly associated with colonoscopy will not be collected. Such events include: Abdominal discomfort, bowel irregularity, bleeding, intestinal perforation, and adverse reaction to the sedation.

Surgical intervention, such as, but not limited to, colectomy and sub-mucosal resection are part of routine patient care for subjects with CRC or AA; therefore, adverse events commonly associated with surgeries will not be collected. Such events include: Bleeding, blood clots in the legs (deep vein thrombosis) and lungs (pulmonary embolism); infection; injury to organs near the colon, such as the bladder and small intestines; and tears in the sutures that reconnect the remaining parts of the digestive system.

AEs will be coded in MedDRA. Type, timing (onset and resolution), relationship, and severity will be of primary interest. In addition to adverse events, related AEs, Serious Adverse Events (SAEs) and Unanticipated Adverse Device Effects (UADEs) will be summarized separately.

### **3.3 Clinical Laboratory Evaluation**

No clinical laboratory evaluations are made for this study.

### **3.4 Vital Signs, Physical Findings, and Other Safety-related Observations**

Weight and height will be collected. No other vital signs, physical findings, or other safety observations are made for this study.

## **4 STUDY DESIGN**

Refer to the study protocol Section 7 for the specific hypotheses to be tested.

### **4.1 Determination of Sample Size**

Refer to the study protocol Section 12.3 for a comprehensive justification for the final sample size.

## **5 CHANGES IN THE CONDUCT OF THE STUDY OR PLANNED ANALYSES**

No changes have been made to the planned analysis delineated in the study protocol.

